**PART 1, VISIT 4**

Subjects should attend Visit 4 wearing the study lenses which were applied at Visit 3 after  $14 \pm 2$  hours. This is the final visit of Part 1.

Visit 4: Treatment 2 Follow-Up (after 14h)		
Step	Procedure	Details
4.1	Adverse Events and Concomitant Medications Review	Review any changes to the subject's medical history or concomitant medications from the previous study visit. Record any changes, and any adverse events.
4.2	Compliance	
Questions regarding the subject's contact lens wear since the previous visit. The number of hours of lens wear, as well as the number of comfortable hours of lens wear will be recorded.
 
N.B. Subjects should not have removed the lenses since the previous visit.
 
If subjects have had to remove one or both lenses, the investigator should stop the visit at

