#### Lid margin staining

# **Clinical Study Protocol**

## **Johnson & Johnson Vision Care, Inc.**

Lid margin staining of the upper and lower eyelids will be performed in the left eye (OS) only using lissamine green. The staining will be graded both subjectively at the time of the clinic visit and also objectively using automated image analysis software from photographs. Images should be collected as soon as possible for best image quality, and grading can be conducted using a slit lamp or from the images.

For the subjective grading the following will be graded for each eyelid:

Horizontal length of staining

Sagittal width of staining

Average staining grade – this is the average of the horizontal and sagittal grades for each eyelid

A final grade will be calculated which is the average of each eyelid's average staining grade.

For the objective image analysis three metrics of staining will be evaluated; (1) Staining Area, (2) Staining Intensity and (3) Staining thickness

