### Non-invasive Break-up Time (seconds)

NIBUT will be measured using the Medmont topographer for the right eye (OD) only. Three measurements will be undertaken.

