# **Clinical Study Protocol**

## **Johnson & Johnson Vision Care, Inc.**

### **4.3. Enrollment Target and Study Duration**

- The overall target is for 54 subjects to complete Part 2 of the study. Approximately 210-240 eligible subjects will be enrolled for Part 1 (Visits 1 and 2). It will be determined based on Visit 2 results whether subjects are suitable to continue in the study. Once the Informed Consent Form signed the subject will be considered enrolled. A replacement will be enrolled if a subject discontinues from the study before completion.
- Approximately 54 subjects (consisting of approximately 27 asymptomatic and 27 symptomatic subjects) will continue to Part 1, Visit 3 to complete all remaining visits.
- The work will be conducted at a single study site and enrollment is expected to take in the region of 12 months. Each subject will attend either a) two visits (Part 1, Visits 1 and 2) if they are not classified as asymptomatic or symptomatic at the end of Part 1, Visit 2 or b) eight visits (all visits in Parts 1 and 2) if they are successfully classified as asymptomatic or symptomatic at the end of Part 1, Visit 2.

The study is expected to last for 18 months in total.

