**Clinical Study Protocol**  
**Johnson & Johnson Vision Care, Inc.**

Visit 4: Treatment 2 Follow-Up (after 14h)		
Step	Procedure	Details
		
this point and a Final Evaluation form should be completed.
 
All subjects are eligible to repeat Visits 3 and 4 of Part 1 on ONE more occasion on a different day if any problems with the lens wear occur between Part 1, Visits 3 and 4. If such problems do occur, Visit 3 will also need to be repeated.

4.3	Subject Reported Ocular Symptoms	Record subject reported ocular symptoms.
4.4	Subjective comfort	Subjective comfort scores for each lens (OD and OS) separately using a vertical VAS scale will be recorded.
4.5	LogMAR visual acuity & over-refraction	Distance high contrast visual acuity will be measured for each eye and binocularly as well as after an over-refraction. The acuity will be recorded to the nearest letter.
4.6	Lens fitting and surface assessment	
Lens fit will be measured using a slit lamp graticule for the following:
 
Coverage:            Nasal coverage            Temporal Coverage            Inferior Coverage            Superior Coverage
 
Centration:            Horizontal centration (by auto calculation)            Vertical centration (by auto calculation)
 
Movement in primary position
 
The lens surface will be recorded according to the following integer scales: lens deposits (0-2), deposit degree (0-4), lens debris (0-4) and lens wettability (0-4).

4.7	Tear height meniscus	
The OD lower tear meniscus will be imaged using the OCT.
 
Three images will be taken.

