**Clinical Study Protocol**  
**Johnson & Johnson Vision Care, Inc.**

Visit 8: Treatment 4 Follow-Up (after 14± 2 hours)			
Step	Procedure	Details	
8.1	Adverse Events and Concomitant Medications Review	Review any changes to the subject's medical history or concomitant medications from the previous study visit. Record any changes, and any adverse events.	
8.2	Compliance	
Questions regarding the subject's contact lens wear since the previous visit. The number of hours of lens wear as well as the number of comfortable hours of lens wear will be recorded.
 
N.B. Subjects should not have removed the lenses since the previous visit.
 
If subjects have had to remove one or both lenses, the investigator should stop the visit at this point and a Final Evaluation form should be completed.
 
All subjects are eligible to repeat Visits 7 and 8 of Part 2 on ONE more occasion on a different day if any problems with the lens wear occur between Part 2, Visits 7 and 8. If such problems do occur, Visit 7 will also need to be repeated.
	
8.3	Subject Reported Ocular Symptoms	Record subject reported ocular symptoms.	
8.4	Subjective comfort	Subjective comfort scores for each lens (OD and OS) separately using a vertical VAS scale will be recorded.	
8.5	LogMAR visual acuity & over-refraction	Distance high contrast visual acuity will be measured for each eye and binocularly as well as after an over-refraction.	Eurolens Research SOP # 12a
8.6	Lens fitting and surface assessment	Lens fit will be measured using a slit lamp graticule for the following:	Eurolens Research SOP # 24

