### **14.9. Procedure for Handling Missing Data and Drop-Outs**

Missing or spurious values will not be imputed. The count of missing values will be included in the summary tables and listings.

Subject dropout is expected to be one of the main reasons of missing data in this clinical trial. Past clinical trials don't provide the evidence that subject dropout is systematic or not-at-random. To evaluate the impact of missing data, sensitivity analysis will be conducted using multiple imputation methods if the proportion of subject dropout is greater than the 15%. The SAS/STAT procedures PROC MI and PROC MIANALYZE will be utilized with a parametric regression method used to make at least 50 imputations.

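### Visits 4 and 8 stop when either lens was removed, so 14-hour data come only from subjects who kept both lenses in, and the 15% dropout trigger is not set by stratum

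*Combined protocol and SAP*

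**What the plan says.** **Stop rule.** Protocol Section 7.2, Visit 4, step 4.2: "If subjects have had to remove one or both lenses, the investigator should stop the visit at" that step; the investigator then fills in the Final Evaluation. Visit 8, step 8.2 repeats it: "If subjects have had to remove one or both lenses, the investigator should stop the visit at this point".

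**Repeat.** The same steps let every subject repeat the study day once; for Part 1 this is "on a different day if any problems with the lens wear occur between Part 1, Visits 3 and 4".

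**Eyes.** Section 2.2 has lid margin staining (LMS) "performed in the left eye (OS) only using lissamine green". For tear break-up time, "NIBUT will be measured using the Medmont topographer for the right eye (OD) only". Tear meniscus height (TMH) and osmolarity are also right eye only.

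**Discontinuation.** Section 4.3: "A replacement will be enrolled if a subject discontinues from the study before completion". Section 8.2 (Withdrawal/Discontinuation), which is distinct from step 8.2, tells the investigator to finish the visit in progress for a discontinued subject.

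**Missing data.** Section 14.9 does not impute in the main analysis. It runs a regression-based multiple imputation only when dropout exceeds 15%, on the ground that "Past clinical trials don't provide the evidence that subject dropout is systematic or not-at-random".

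**The concern.** The strata are defined by lens discomfort (CLDEQ-8), and discomfort is a plausible reason for taking a lens out before 14 hours. A rule that ends data collection on removal can therefore select on the trait under study. It also takes more than it needs to: with only the right lens out, left-eye staining could still be graded; with only the left lens out, the three right-eye measures could still be taken. The comfort score is not taken in either case, which trims the low end of the comfort range used in the secondary correlations (Section 14.6).

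Replacement restores the count but not the type of subject who left. If the loss falls mainly on uncomfortable symptomatic wearers, the 14-hour comparison could be pulled toward no difference, and a trigger that is not set by stratum may not reveal it.

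**Working it through.** **1. What the stop removes.** At Visit 4 the steps after 4.2 are symptoms (4.3), comfort (4.4), TMH (4.7), NIBUT (4.8), osmolarity (4.9) and LMS (4.14). The Final Evaluation holds only a form, slit lamp and acuity. So four of the five primary measures are not collected. The fifth, white blood cell density, was taken at Visit 2 (Visit 6 in Part 2). Adverse events (4.1), hours worn and comfortable hours (4.2) are recorded before the stop.

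**2. The plan's own power figure.** Table 10 gives 81% for an LMS difference of 0.35, SD 0.5, 27 per stratum. A two-sample t-test with one-sided 5% alpha gives 81.4%, so the figure reproduces. (Two-sided 5% gives 71.4%; that mismatch with Section 14.4 is a separate matter.)

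**3. Loss of numbers alone, no replacement.** Losing 10%, 20% or 30% of the symptomatic stratum (27 falls to 24, 22 or 19) gives power of 79.3%, 77.5% or 74.4%. This cost is modest.

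**4. Selection, stratum refilled to 27.** The documents give no removal rate, so this is a range under assumptions. Let f be the share of symptomatic subjects who never reach 14 hours, assumed the least tolerant, and rho the correlation of intolerance with the measure. The symptomatic mean moves toward the asymptomatic mean by rho × phi(z_f)/(1 − f) SD. The asymptomatic mean and the SD are held fixed.

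| f | rho | shift (SD) | LMS difference left | power |
|---|---|---|---|---|
| 5% | 0.2 to 0.6 | 0.022 to 0.065 | 0.339 to 0.317 | 79.2% to 74.4% |
| 10% | 0.2 to 0.6 | 0.039 to 0.117 | 0.331 to 0.292 | 77.4% to 68.1% |
| 20% | 0.2 to 0.6 | 0.070 to 0.210 | 0.315 to 0.245 | 73.9% to 55.3% |

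Example: f = 10%, rho = 0.2 gives 0.2 × 0.1755/0.9 = 0.039 SD, and 0.35 − 0.5 × 0.039 = 0.331.

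**5. Effect of the repeat day.** If 20% fail the first day and 25% to 75% of those fail again, permanent loss is 0.20 × 0.25 = 5% to 0.20 × 0.75 = 15%, or 1.4 to 4.1 of 27.

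**6. The only empirical anchor.** Table 4 shows 42 enrolled and 25 + 16 = 41 completed in the earlier study with this lens. If the one loss was symptomatic, that is 1/17 = 5.9%, close to the 5% row.

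**7. The 15% trigger.** Section 14.9 does not define its denominator; I take the 54 continuing subjects. Then 15% × 54 = 8.1.
- 8 losses, all symptomatic, not replaced: 8/54 = 14.8% overall, 8/27 = 29.6% of the stratum.
- The same 8 replaced: 8/62 = 12.9% overall, 8/35 = 22.9% of the stratum.
- The most that stays under 15% with replacement: 9/63 = 14.3% overall, 9/36 = 25% of the stratum.

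**8. What fellow-eye data would recover.** At 20% removal (5.4 of 27), with half one-sided and split evenly between eyes, 5.4 × 0.5 × 0.5 = 1.35 subjects stay evaluable for the right-eye measures and 1.35 for LMS.

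**The case against.** The strongest defence is that this is a study of bilateral wear and its hypotheses concern subjects after 14 hours of it. Someone wearing one lens is outside that condition, so requiring both lenses is a defensible choice. First-attempt values from one eye combined with a repeat day for the other would also mix days and baselines, since Visit 3 is repeated too. This stands as a reason not to make first-attempt fellow-eye values the primary data when a repeat exists. It is not a reason to leave them uncollected.

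Selection for tolerance also starts earlier. Subjects agree to long daily wear at entry and wear this lens for two weeks before Visit 2. The repeat day reduces permanent loss further, and nearly everyone completed the earlier study. These points stand and limit the likely size.

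Fellow-eye data recover few subjects, and nothing from anyone who removed both lenses. A per-stratum trigger alone would only run the same imputation, which assumes missing at random. Both points stand and shape the fix.

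A reader might infer that bias toward no difference is established. It is not: the rule applies to both strata and to removal for any reason, and the documents give no removal rates. A reader might also infer that about 30% of the symptomatic stratum could be lost unnoticed; that ignores replacement, under which the ceiling is 25%.

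**Conclusion.** The point holds in limited form. The four 14-hour primary measures and the 14-hour comfort score come only from subjects who kept both lenses in on at least one of two attempts. Usable measures in an eye that kept its lens are not collected, and no planned analysis would reliably expose a discomfort-driven loss in one stratum.

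Understatement of the difference between strata is plausible, not demonstrated. Its size rests on an assumed loss and correlation. Near the earlier study's completion rate, LMS power would fall from 81.4% to roughly 74% to 79%; a 20% permanent loss would be needed for 55% to 74%. It would be wrong to read the rule as costing all five primary endpoints, since the white blood cell measure is collected before the rule can apply.

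The documents also conflict: steps 4.2 and 8.2 stop the visit, while Section 8.2 has the investigator finish it for a discontinued subject. A Final Evaluation form is also called for even though a repeat is permitted. These passages must be reconciled. The change is cheap and worth making; the point does not undermine the design.

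**What to change.** 1. Reconcile steps 4.2 and 8.2 with Section 8.2, and state when the Final Evaluation form applies if a repeat is planned.
2. When one lens was removed, complete the already scheduled measures in the eye that kept its lens. In every case record symptoms, comfort, and the time of and reason for removal. This concerns data collection only and changes no lens-wear rule.
3. Use the completed repeat day in the primary analysis when there is one. Use first-attempt fellow-eye values in a pre-specified sensitivity analysis, or when no repeat is completed.
4. Report removals and repeats by stratum, with reasons.
5. In Section 14.9, define the dropout denominator, apply the 15% trigger within each stratum, and add a not-at-random sensitivity analysis (for example delta-adjusted), since the planned regression imputation assumes missing at random.

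Cost: protocol, eCRF and SAP wording, and slightly more analysis. No new procedure is needed. Some subjects will contribute to some endpoints and not others.

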**Clinical Study Protocol**  
**Johnson & Johnson Vision Care, Inc.**

Visit 4: Treatment 2 Follow-Up (after 14h)		
Step	Procedure	Details
		
this point and a Final Evaluation form should be completed.
 
All subjects are eligible to repeat Visits 3 and 4 of Part 1 on ONE more occasion on a different day if any problems with the lens wear occur between Part 1, Visits 3 and 4. If such problems do occur, Visit 3 will also need to be repeated.

4.3	Subject Reported Ocular Symptoms	Record subject reported ocular symptoms.
4.4	Subjective comfort	Subjective comfort scores for each lens (OD and OS) separately using a vertical VAS scale will be recorded.
4.5	LogMAR visual acuity & over-refraction	Distance high contrast visual acuity will be measured for each eye and binocularly as well as after an over-refraction. The acuity will be recorded to the nearest letter.
4.6	Lens fitting and surface assessment	
Lens fit will be measured using a slit lamp graticule for the following:
 
Coverage:            Nasal coverage            Temporal Coverage            Inferior Coverage            Superior Coverage
 
Centration:            Horizontal centration (by auto calculation)            Vertical centration (by auto calculation)
 
Movement in primary position
 
The lens surface will be recorded according to the following integer scales: lens deposits (0-2), deposit degree (0-4), lens debris (0-4) and lens wettability (0-4).

4.7	Tear height meniscus	
The OD lower tear meniscus will be imaged using the OCT.
 
Three images will be taken.

**Clinical Study Protocol**  
**Johnson & Johnson Vision Care, Inc.**

Visit 4: Treatment 2 Follow-Up (after 14h)			
Step	Procedure	Details	
4.8	Non-invasive tear break-up time	OD tear film break up time will be measured using the Medmont topographer  Three measurements will be undertaken.	Eurolens Research SOP # 16
4.9	Tear film osmolarity	OD osmolarity measured using the Tearlab.  Two measurements will be undertaken.	Eurolens Research SOP # 52
4.10	Tear sample collection	OD; 2µl tear sample will be collected using a glass capillary tube before application of any dyes to the ocular surface.  Tears will be collected over a maximum period of 15 minutes.	Eurolens Research SOP # 57
4.11	Lens removal	Lenses will be removed and discarded.	
4.12	Subjective comfort	Subjective comfort scores using a vertical VAS scale will be recorded for each eye separately.	
4.13	Slit lamp biomicroscopy	OD: Full biomicroscopy. Grades will be scored to the nearest 0.1 in the best judgment of the investigator using Efron Grading Scales for both eyes.  OS: white light exam only. NO LID EVERSTON	Eurolens Research SOP #13
4.14	Ocular surface and lid margin staining photography and grading	OS: Sodium fluorescein will be added to the ocular surface and the following will be graded using Efron scales: corneal and bulbar conjunctival staining.  OS ONLY: Lissamine green will then be added to the ocular surface and photographs of the upper and lower lid margin staining will be taken. These images will be used to subjectively grade lid margin staining at the time of the visit and for subsequent automated image analysis.  OS: after all lissamine green assessments have been completed, the eyelid will be everted and the palpebral conjunctiva will be graded using Efron Grading scales.	Eurolens Research SOP #13  Eurolens Research SOP #41

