### **2.2. Endpoints**

Primary Endpoint(s)

The primary endpoints in this study are lid margin lissamine green staining grade, NIBUT, TMH, tear film osmolarity at the beginning and the end of a lens-wearing day (after 14 hours). Additionally, the number of white blood cells in the lid margins after 6 hours of lens wear will be investigated.

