### **5.2. Masking**

This is an open label study where the identity of the lenses used is known to all. However, both subjects and investigators involved with data collection will be masked as to which group (asymptomatic or symptomatic) they have been assigned to following Part 1, Visit 2.

Under normal circumstances, the mask should not be broken until all subjects have completed the study and the database is finalized. Otherwise, the mask should be broken only if specific emergency treatment/course of action would be dictated by knowing the treatment status of the subject. In such cases, the Investigator may, in an emergency, contact the medical monitor. In the event the mask is broken, the Sponsor must be informed as soon as possible. The date, time, and reason for the unmasking must be documented in the subject record. The Investigator is also advised not to reveal the study treatment assignment to the clinical site or Sponsor personnel.

Subjects who have had their treatment assignment unmasked are expected to return for all remaining scheduled evaluations. Subjects who are discontinued will be replaced.

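### Lid margin staining, a primary endpoint, is graded subjectively at the visit after comfort and symptoms have been recorded, which weakens the stated masking in the direction of Hypothesis 1

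*Combined protocol and SAP*

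**What the plan says.** Section 2.2 makes staining a primary endpoint: "The primary endpoints in this study are lid margin lissamine green staining grade, NIBUT, TMH, tear film osmolarity" and white cell density. On how it is assessed, the same section says: "The staining will be graded both subjectively at the time of the clinic visit and also objectively using automated image analysis software from photographs". It leaves the source of the subjective grade open, since "grading can be conducted using a slit lamp or from the images". For the software it adds: "For the objective image analysis three metrics of staining will be evaluated", namely area, intensity and thickness.

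Section 5.2 states that "both subjects and investigators involved with data collection will be masked as to which group (asymptomatic or symptomatic") a subject belongs to. In line with this, the CLDEQ-8 at Visit 2 (step 2.6) is completed with the investigator masked.

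The order of steps at Visit 4 (Section 7.2) is:
- 4.2, compliance: "the number of comfortable hours of lens wear will be recorded";
- 4.3: "Record subject reported ocular symptoms";
- 4.4: VAS comfort with lenses in;
- 4.12: VAS comfort after lens removal;
- 4.14: dye, photographs and grading, where "These images will be used to subjectively grade lid margin staining at the time of the visit and for subsequent automated image analysis".

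Visit 8 has the same order (8.2, 8.3, 8.4, 8.12, then 8.13). Section 14.5 builds both staining models on the horizontal and sagittal grades and contains no model for the automated metrics.

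**The concern.** Section 4.1 keeps only subjects scoring 10 or less, or 20 or more, on the CLDEQ-8. Whoever is examined at Visit 4 is therefore known to come from one end or the other, and a grader who wished to guess has two options. Comfortable hours, symptoms and comfort scores are the kind of information that helps such a guess. The investigator acts at step 4.2, and SOP #41 (Appendix M) assigns lid assessment to clinical investigators. Nothing in the protocol separates the two tasks or hides identity on the images.

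Hypothesis 1 predicts more staining in symptomatic subjects. A grader who shares that expectation would err towards it, so the risk is a false-positive result on one of the five primary measures.

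**Working it through.** **The plan's own figure first.** Inputs: 27 per stratum (Section 14.2); effect 0.35 and SD 0.5 (Table 10); one-sided 95% interval (Section 14.5). Two-sample t-test with 2 × 27 − 2 = 52 degrees of freedom:

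- standard error = SD × √(2/27) = 0.5 × 0.2722 = 0.1361
- noncentrality = 0.35 / 0.1361 = 2.57
- one-sided 5% power from the noncentral t = 81.4%; Table 10 states 81%.

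All nine cells of Table 10 reproduce this way. A two-sided 5% test does not reproduce them (71.4% for this cell), so the one-sided calculation is used below.

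**What a grading bias would do.** Suppose the strata do not differ, but symptomatic subjects are over-graded by an average of b relative to asymptomatic subjects. The test then has noncentrality b / (SD × √(2/27)), and its rejection rate is the false-positive rate. The documents give no value of b; those below are assumptions. The SDs are the three in Table 10.

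| Assumed b | SD 0.5 | SD 0.7 | SD 0.9 |
|---|---|---|---|
| 0 | 5.0% | 5.0% | 5.0% |
| 0.05 | 10.0% | 8.3% | 7.4% |
| 0.10 | 17.9% | 13.0% | 10.7% |
| 0.20 | 42.3% | 27.1% | 20.1% |

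For b = 0.10 the noncentralities are 0.10/0.1361 = 0.73, 0.10/0.1905 = 0.52 and 0.10/0.2449 = 0.41. The bias that doubles the error to 10% is 0.05, 0.07 or 0.09 grade at the three SDs. At the two-sided 5% level stated in Section 14.4, b = 0.10 gives 11.1%, 8.1% and 6.9%.

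**Which SD is relevant.** The historical 14-hour SDs in Table 5 run from 0.72 to 0.89 per lid, nearer the right-hand columns. The average of two lids may vary less.

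**What b = 0.10 means in practice.** The final grade averages four component grades (two scales, two lids). One grade on one component in one subject moves that subject's final grade by 1/4 = 0.25. A mean bias of 0.10 thus corresponds, for example, to a net one-grade rise on one component in 0.10/0.25 = 40% of symptomatic subjects (about 11 of 27) and none in the other stratum.

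**Baseline adjustment.** Both models adjust for baseline staining. If the bias is b0 at baseline and b at 14 hours, and the baseline slope is β, then b − β × b0 remains. The baseline grade (step 3.10) also follows a comfort score (step 3.2), so a tendency present at both visits is partly absorbed. Fewer cues precede grading at Visit 3 than at Visit 4, so b0 may be smaller than b. The documents give neither β nor b0.

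**The case against.** A reader might infer that the visit order undoes the masking. The documents do not show that. The mask covers the stratum assigned from the Visit 2 questionnaire, which the investigator does not see. Visit 4 uses other measures, and its study day may fall 2 to 180 days after Visit 2. Nothing states that the person who records comfort also grades staining, and no figure shows how well Visit 4 comfort predicts stratum. What stands is that the grader may infer the stratum and that nothing in the plan prevents it.

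A reader might also take 0.25 as a plausible group bias because one component step equals 0.25. That step belongs to one subject; a mean bias of 0.25 would need a net one-grade shift averaged over the whole symptomatic stratum.

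The grading is anchored. SOP #41 sets cut-points in millimetres of length and percentage of lid-wiper width, which leaves less room for impression. Together with the baseline adjustment, this limits the bias but does not remove it.

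The automated metrics might look like a clean check. They are only less exposed: SOP #41 requires the lid margin to be outlined by hand first, with no masking of that operator described. Section 14.1 defers detail to a stand-alone SAP, so absence from Section 14.5 does not prove that no analysis is planned.

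Moving the comfort and symptom questions after the staining step might seem the natural remedy. It does not fit the visit. The wear questions at 4.2 decide whether the visit proceeds, the lens-comfort score must precede lens removal at 4.11, and Section 1.4 lists temporary discomfort from both dyes, which would affect symptoms asked afterwards.

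Finally, the design is kept close to an earlier study for a later meta-analysis (Section 4.2). Grading the same photographs on the same scale at a later time should affect that little.

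**Conclusion.** The point holds as a weakness in masking, not as a failure of it. The primary staining models rest on a judgement made at the visit, after information related to stratum has been recorded, with no separate grader and no coded images described. The direction of any bias favours Hypothesis 1. Its size is unknown. Under an assumed mean differential of 0.10 grade, the false-positive rate would be about 18%, 13% or 11% across Table 10's SDs instead of 5%. This rests on an unadjusted one-sided t-test with 27 per stratum and no true difference. The figures show sensitivity and are not evidence that a bias exists. The change should be made, because the protection is available from photographs that are already planned.

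**What to change.** 1. Keep the photography at steps 3.10, 4.14, 7.10 and 8.13 as planned. Have the existing graders grade the images in a later session, with subject, visit and stratum identifiers removed and in random order across subjects and visits, which also limits recall. Use that grade, at baseline and at 14 hours, in Models 1 and 2.
2. In Section 2.2, remove the slit-lamp alternative for the grade that enters the analysis.
3. Pre-specify the automated staining area as a supportive analysis of Hypothesis 1, with the lid outline also drawn on coded images. Area is listed both in Section 2.2 and in SOP #41.
4. Leave the order of the visit steps unchanged.

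Cost: relabelling, one later grading session by the same staff, and one further model. Staining grades would not be available on the visit day, but no continuance decision uses them: those depend on the CLDEQ-8, slit lamp findings, lens fit and acuity. Sample size, test level and the power in Table 10 are unaffected.
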